**Overview of the study.** We will determine the effects of HAI on reducing anxiety, depression, worry, and pain and enhancing QoL in children (n=30) (ages 8-17 years) with a LTC and their parent caregivers (n = 30-60). Human-animal interactions will involve visits from a registered canine team for 10-15 minutes during each child's potentially anxiety-producing appointments at the clinic or hospital. These appointments occur approximately once/week: Children and parent dyads will receive HAI intervention and complete measures of anxiety, depression, worry, pain and QoL at baseline, 4 weeks and at the end of the study (8 weeks).

**Eligibility Criteria and Recruitment.** Our sample target is 30 children diagnosed with advanced cancer and their parents/guardians. We will oversample to conservatively accommodate a drop-out of up to 35%, thus our accrual target sample is 48 children and parent/guardian pairs. Inclusion criteria for children are: 1) ages of 8-17 years, 2) diagnosed with advanced cancer as defined by any stage of relapsed, recurrent or refractory cancer as indicated by healthcare team and 3) able to understand English or Spanish to complete consents and surveys. Inclusion criteria for caregivers are: 1) parent or guardian as determined by person who brings child to >50% of their clinic visits, and 2) able to understand English or Spanish to complete consents and surveys. Inclusion criteria for animal therapy teams are: 1) registered Pet Partners or other nationally recognized agency team, 2) owner able to speak and understand English or Spanish, 3) owner who has successfully completed volunteer training at Vanderbilt University Medical Center.

Exclusion criteria for both children and caregiver include a self-reported fear of or allergies to canines or cognitive impairment as identified by healthcare team or inability to complete consenting process. Recruitment and enrollment for this study will occur over 18 months. In collaboration with each child's nurse practitioner or physician, our team will determine families eligible for the study. Final decisions regarding screening and inclusion will be determined by the PI. Approximately 200 children 8-17 years are diagnosed with cancer at MCJCHV each year and about 40 have advanced cancer. In our past study with children diagnosed with cancer, only 2 families (3.5%) of 58 families approached declined to participate with no attrition. We anticipate refusals and attrition may be higher with this population, so are very conservative in our estimates (Table 1).

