**Table 1. Estimates of Children Meeting Inclusion Criteria and Recruitment Rates**

Children Ages 8-17 Years with Advanced Cancer at MCJCHV	Total Per Year	Total 18 Months
Number of eligible participants per year	32	48
T1: Accrual (96% in previous studies, conservative estimate for this population is 85%)	27	40
End of Study: Retention (95% in previous studies, but conservative estimate for this population is 75%)	20	30

**Setting.** All study activities including procedures and data collection will take place in the treatment room in the hematology/oncology clinic or a private room at MCJCHV and will occur approximately weekly. Sessions will coincide with children and families' scheduled medical appointments or inpatient hospitalizations.

**Procedures.** After potential participant families are identified and screened for inclusion/exclusion criteria, the PI or project coordinator will meet with the primary caregiver, introduce the study, and review the IRB-approved consent. If the parent/guardian agrees, the child will be approached for assent. Participants will then be asked to complete baseline measures. Human-Animal Interactions will occur at each clinic visit or hospitalization, as long as they are not more frequent than weekly. Data collection will occur at baseline, 4 weeks, and study end (8 weeks) with children and parents completing surveys in private sections of the room. All study data will be stored in REDCap, a secure, web-based application for building and managing databases. Tablets will be used by study participants to enter their responses to study measures into their study record in REDCap. Paper forms will be available to participants if there is a problem with network connectivity or if the participant prefers that form. Subsequently, data on paper forms will be double-entered into the participant's record in REDCap by trained study staff and verified.

**Human-Animal Interactions (HAI).** Every effort will be made to ensure the same dog is used consistently with each family, but a back-up team will be available in the event the HAI team is ill or unavailable. The HAI consists of the following: 1) *Social Interaction*: participants will be guided by the canine owner in interfacing with

Version approved by IRB 11-18-2019

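### The text sets an accrual target of 48 pairs, but Table 1 counts 48 as every eligible child over the same 18 months and expects to accrue 40

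*Combined protocol and SAP*

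**What the plan says.** All references are to the combined protocol and SAP. The section Eligibility Criteria and Recruitment sets a target of 30 children and then says: "We will oversample to conservatively accommodate a drop-out of up to 35%, thus our accrual target sample is 48 children and parent/guardian pairs". It fixes the period: "Recruitment and enrollment for this study will occur over 18 months". On the size of the source population it says: "Approximately 200 children 8-17 years are diagnosed with cancer at MCJCHV each year and about 40 have advanced cancer". For experience so far it cites an earlier study by the team in which "only 2 families (3.5%) of 58 families approached declined to participate with no attrition". It then warns that refusal and attrition may be worse here, and points to Table 1 for its cautious estimates.

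Table 1 has three rows:

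| Row | Per year | 18 months |
|---|---|---|
| "Number of eligible participants per year" | 32 | 48 |
| Accrual, at 85% | 27 | 40 |
| Retention at study end, at 75% | 20 | 30 |

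Under Summary, Limitations, and Future Directions, the sample size is justified by how many families it is realistic to recruit and follow. No power calculation is given.

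**The concern.** The number 48 carries two labels for the same site, population and 18 months. In the text it is the number of pairs to be enrolled. In Table 1 it is the number of eligible children before any family has been asked. The two agree only if nobody refuses, and the plan itself expects refusals.

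The loss assumptions differ as well. The text allows for up to 35% drop-out; Table 1 plans on 25%. Both are described as conservative.

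As a result, a reader cannot tell whether enrolling 40 pairs is on plan or 8 short. This has some bearing on Aim 1, which sets out to obtain recruitment estimates; Table 2 also lists recruitment rate and attrition as feasibility measures. No numerical Aim 1 threshold is stated, so none is breached, but the planning figures against which recruitment would be read do not agree.

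**Working it through.** **Inputs.** From the text: 30 completers, up to 35% drop-out, accrual target 48, 18 months, about 40 children a year with advanced cancer, and 2 refusals among 58 families in the earlier study. From Table 1: 32 eligible a year, 85% accrual, 75% retention, and 18-month counts of 48, 40 and 30.

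**1. The text's figure.** Enrolment needed = 30 / (1 − 0.35) = 46.15, rounded up to 47. The stated 48 is one above this. In the other direction, 48 × 0.65 = 31.2 completers. So 48 is a reasonable enrolment number for 30 completers at 35% drop-out.

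**2. Table 1's figures.**
- Eligible: 32 × 1.5 = 48.
- Accrued: 48 × 0.85 = 40.8, stated as 40.
- Retained: 40 × 0.75 = 30 (unrounded, 48 × 0.85 × 0.75 = 30.6).

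Table 1 is also internally sound.

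**3. The two together.**
- Uptake needed to accrue 48 of 48 eligible: 48 / 48 = 100%.
- Eligible children needed to accrue 48 at 85%: 48 / 0.85 = 56.5, so 57, against 48 in Table 1.
- Difference in accrual: 48 − 40 = 8, or 8 / 48 = 17% of the text's target.

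**4. Past uptake.** In the earlier study 56 / 58 = 96.6% agreed. Applied to 48 eligible, this gives 48 × 0.966 = 46.3 accrued, still below 48. After 35% drop-out, 46.3 × 0.65 = 30.1 remain. The text's tolerance therefore just holds if uptake matches the earlier study; the minimum is 46.15 / 48 = 96.2%. The plan expects more refusals here and uses 85%.

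**5. What Table 1's accrual can absorb.** The largest drop-out that leaves 30 of 40 is 1 − 30/40 = 25%. At 35%, 40 × 0.65 = 26 completers.

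**6. Is 35% a combined loss?** Refusal and attrition together at Table 1's rates: 1 − 0.85 × 0.75 = 36.25%. From its rounded counts: 1 − 30/48 = 37.5%. Both are near 35% and slightly above it. On this reading 48 is the number eligible, as Table 1 says, and the text has mislabelled both figures.

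**7. Is the pool larger than 48?** About 40 a year over 18 months is 40 × 1.5 = 60 children with advanced cancer. Table 1 counts 32 / 40 = 80% of these as eligible, which is again 48. This supports Table 1's label.

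**The case against.** The strongest reply is that a target and a forecast need not be equal. The text gives a goal with a worst-case drop-out, while Table 1 gives deliberately pessimistic estimates. A target above a cautious projection, and an upper bound of 35% beside a planning value of 25%, are not contradictory in themselves. Table 1's 48 is also an estimate and not a hard ceiling: if 57 of the roughly 60 children with advanced cancer proved eligible, 85% uptake would give 48.

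Part of this stands. The shortfall depends on Table 1's eligible count, and accruing 48 is not impossible in an absolute sense. But the text does not present 48 as a ceiling or an aspiration; it derives it from drop-out. A target that needs every eligible family to agree does not fit a plan that expects more refusals and justifies its size by what is realistic. Assuming 57 eligible would replace the only eligibility estimate given and so contradict Table 1 in another row.

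A second reply is that the documents do not show which passage is right, so Table 1 should not simply be preferred. The documents indeed do not say what was intended. Table 1 is the better anchor because it separates refusal from attrition, agrees with the stated caseload, and is the source the text cites. Its preference does have a cost, set out under the fix.

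A third reply is that nothing in the analysis uses 40 or 48. That is correct, and it limits the severity without removing the discrepancy.

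**Conclusion.** The discrepancy holds and is minor. The accrual target in the text exceeds the accrual in the plan's own recruitment table by 8 pairs (48 against 40), and the drop-out allowance differs by 10 percentage points (35% against 25%). At Table 1's accrual, the claimed 35% tolerance would leave 26 completers, 4 below target.

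This rests on Table 1's 48 eligible and 85% uptake, and on reading 35% as loss after enrolment, which is what the text says. If 35% was meant as refusal plus attrition, the arithmetic roughly fits, but 48 is then wrongly called accrual and 35% wrongly called drop-out. The target of 30 completers is unchanged, and no endpoint, power statement or safety rule is affected.

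**What to change.** Reword the sentence on oversampling to follow Table 1: about 48 eligible children over 18 months, about 40 pairs accrued at 85% uptake, and 30 expected completers at 25% drop-out. Then settle the 35% in one of two ways:

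- If it meant drop-out after enrolment, remove the claim, because 40 accrued cannot lose more than 25% and still leave 30.
- If it meant total loss from eligible to completer, say so and give it as about 36% (36.25% from the rates; 37.5% from the rounded counts).

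The cost is one reworded sentence. The target of 30 and the 18-month recruitment period need not change for this purpose. Under the first option the plan gives up its stated tolerance for drop-out above 25%. If the investigators want to keep 48 accrued and 35%, they would instead have to revise Table 1 and justify either about 57 eligible children at 85% uptake or uptake of 100% among 48.

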**Table 1. Estimates of Children Meeting Inclusion Criteria and Recruitment Rates**

Children Ages 8-17 Years with Advanced Cancer at MCJCHV	Total Per Year	Total 18 Months
Number of eligible participants per year	32	48
T1: Accrual (96% in previous studies, conservative estimate for this population is 85%)	27	40
End of Study: Retention (95% in previous studies, but conservative estimate for this population is 75%)	20	30

**Setting.** All study activities including procedures and data collection will take place in the treatment room in the hematology/oncology clinic or a private room at MCJCHV and will occur approximately weekly. Sessions will coincide with children and families' scheduled medical appointments or inpatient hospitalizations.

**Procedures.** After potential participant families are identified and screened for inclusion/exclusion criteria, the PI or project coordinator will meet with the primary caregiver, introduce the study, and review the IRB-approved consent. If the parent/guardian agrees, the child will be approached for assent. Participants will then be asked to complete baseline measures. Human-Animal Interactions will occur at each clinic visit or hospitalization, as long as they are not more frequent than weekly. Data collection will occur at baseline, 4 weeks, and study end (8 weeks) with children and parents completing surveys in private sections of the room. All study data will be stored in REDCap, a secure, web-based application for building and managing databases. Tablets will be used by study participants to enter their responses to study measures into their study record in REDCap. Paper forms will be available to participants if there is a problem with network connectivity or if the participant prefers that form. Subsequently, data on paper forms will be double-entered into the participant's record in REDCap by trained study staff and verified.

**Human-Animal Interactions (HAI).** Every effort will be made to ensure the same dog is used consistently with each family, but a back-up team will be available in the event the HAI team is ill or unavailable. The HAI consists of the following: 1) *Social Interaction*: participants will be guided by the canine owner in interfacing with

Version approved by IRB 11-18-2019

the dog and 2) *Activities*: participant-selected activities from a core group of 22 activities such as petting the dog and talking to the dog, chosen by Pet Partners to constitute the foundation for HAI. Pet Partners is a non-profit organization that assists individuals to maintain their health or regain their full potential through HAI. Activities used represent integration of interactions into a child's treatment plan. Implementation fidelity of intervention and receipt of intervention will be determined by documentation by the animal handler, a trained research assistant, and the PI after reviewing the video recordings of HAI.

**Implementation Fidelity**: As recommended by the NIH Behavior Change Consortium, we will use 5 key factors to enhance HAI fidelity: study design, provider training, HAI delivery, treatment receipt (patient understands or is able to use the new skills), and enactment (patient treatment skills in the intended situations and at the appropriate time). In addition to following the activity log developed by Pet Partners for the HAI, we will maximize fidelity through 1) comprehensive initial training for all canine owners, 2) reviewing videos recorded at each session, 3) monthly research team meetings to review recruitment, protocol activities, and

intervention fidelity, 4) content analyses of interviews and 5) re-training as necessary. *Safety*: Any evidence of aggressive behavior by the dogs will be carefully monitored and the interaction will end immediately with the removal of the dog from the premises. At the end of a family's 2-month participation in the study, we will ask children and parents separately: "Please describe what it was like to participate in this project." Results will provide a positive transition at study end and offer feedback and potential revisions to be used in the next study. Children will receive a stuffed dog at the conclusion of the study to provide continued support when they transition away from HAI.

**Measures.** Measures are described here and in Table 2 according to specific aims.

**Aim 1:** Examine feasibility of HAI sessions for children with a LTC and a primary caregiver, specifically to: a) identify and document necessary modifications for a safe and feasible intervention, b) obtain recruitment estimates and determine potential recruitment barriers, c) evaluate elements of implementation fidelity (design, training, delivery/receipt of treatment, enactment), and d) verify safety.

*Safe and feasible intervention:* Safety verification will be determined by documentation of any evidence of potential risk for injuries encountered during the sessions. Handler and Site Coordinator Self-Report Measure/Animal-Assisted Therapy (AAT) Activity Log is a checklist for recording people present and activities conducted during session to be completed after each session. *Recruitment estimates and potential barriers to recruitment:* Screening Checklist includes numbers of children meeting inclusion criteria, number recruited, and barriers.

**Aim 2:** Determine the preliminary efficacy of HAI sessions for 1) children with a LTC for the outcomes of QoL, anxiety, depression, worry, and pain, 2) caregivers of children with a LTC for the outcomes of stress and anxiety.

The Family Demographic Form has 14 items including questions about age, race, gender, diagnosis, family members and pet ownership. Similar to other studies and as used in our previous studies, anxiety will be measured using the 20-item STAI for Children. This questionnaire has been used extensively in school-aged children (Cronbach's  $\alpha = .82-.87$ ). Health-related Quality of Life will be measured by the PedsQL Generic (Cronbach's  $\alpha = .88$ ) and Cancer (.72) report forms. The PedsQL is a 23-item (general) or 27 item (cancer) health-related quality of life questionnaire for child self-report. This study will use the Child Self Report and Parent Proxy versions for ages 8-12 and 13-17. The multidimensional scales include physical (5 items), emotional (4 items), social (3 items), and school functioning (3 items) dimensions with scores of 0-4 for each item for the general Peds QoL, and 8 dimensions (pain-2 items, nausea-5 items, procedural anxiety-3 items, treatment anxiety-3 items, worry-3 items, cognitive-3 items, perceived physical appearance-3 items, and communication-3 items) for the cancer Peds QoL. *Caregiver:* The Pediatric Quality of Life (PedsQL) Generic Parent (Cronbach's  $\alpha = .93$ ) and Cancer (.87) inventories have parent report forms that range from 21-27 items. The State-Trait Anxiety Inventory (STAI) Adult Form assesses primary caregivers' anxiety, has a reported Cronbach's  $\alpha$  ranging from .78-.82 and includes 20 items in Likert format to assess trait characteristics and 20 items for state anxiety. A brief new measure of depression from the Patient Reported Outcomes Measurement Information System (PROMIS) with strong psychometrics has been added for child self-report and parent-proxy (Cronbach's  $\alpha = .80$ ).

**Exploratory Aim:** To explore mechanisms (reduced salivary cortisol and urinary norepinephrine levels) associated with 8 weeks of HAI.

*Mechanisms and biomarkers:* As part of our exploratory aim we will measure salivary cortisol and 24 hour urinary norepinephrine (NE) levels. Studies have shown that increase in salivary cortisol and urinary NE correlate to increased levels of acute stress. Similar to the methods of Corbett et al. salivary swabs will be obtained at baseline at 10:00 am and 2:00 pm before HAI and 30 minutes after HAI on week 4 and week 8 of the study. Attempts will be made to schedule appointments between 10:00 am and 2:00 pm to control for circadian variations. Saliva will be obtained and stored ((-80°C) until time of analysis in the Vanderbilt Hormone Analytical Services Core. Urinary NE will be measured from 24-hour urine collections obtained at baseline, midway, and toward the end of the study. Twenty-four hour (NE24) levels will be used as an indirect measure of stress and adrenergic activation. Urinary creatinine levels will confirm compliance with 24-hour collections, and variations in volume. NE values will be compared to normative ranges for sex, ethnicity, and BMI. NE will be measured by high performance liquid chromatography (Quest diagnostics). Although not primary outcomes, we will measure heart rate/blood pressure, using a calibrated Dynamap monitoring device. Evidence from our work with newly diagnosed cancer patients indicates anxiety and worry may begin to

increase at the time families realize the HAI sessions are ending. Therefore as noted above, we will obtain these measures at baseline, mid-way at 4 weeks, and at the end of the 8 week study. Part of Aim 1 is to determine the feasibility of the HAI intervention, especially the most reliable time to obtain these measures.

**Table 2. Measures and Schedule**

Variable	Measure	# items/Scoring Range Clinical Significance	Time to Complete	Schedule
AIM 1			Minutes	
Safety/Feasibility	AAT Activity Log	22 items	5	After each HAI
Feasibility	Recruitment Rate, Attrition			Consent/assent. After final HAI
Intervention	Videotaping of All Sessions		15	During each HAI
AIM 2				
Anxiety – Trait	State-Trait Anxiety Inventory for Children (STAIC) Trait Form	20 items/20-80; Clinical significance 39-40	5	Baseline
Anxiety – State	STAIC State Form	20 items/20-80; Clinical significance 39-40	5	Baseline, 4 & 8 wks
QoL	PedsQL-General	23 items/range 0-92	15	Baseline, 4 & 8 wks
	Peds QL-Cancer	27 items/range 0-108		Baseline, 4 & 8 wks
HR and B/P	Heart Rate and B/P Log		2	Baseline, 4 & 8 wks
Depression	PROMIS Depressive Symptoms	8 items	2	Baseline, 4 & 8 wks
Acute Stress	Salivary Cortisol		3	Baseline, 4 & 8 wks
	Urinary NE, creatinine		20	Baseline 4 & 8 wks
HAI Perceptions	Open-Ended Interview	Semi-Structured	15	End of Study
	Parent Family Demographic Form	14 items	10	Baseline
Child QoL	PedsQL General and Cancer-Parent Proxy	26 items	5	Baseline, 4 & 8 wks
Anxiety – Trait	STAI – Trait Form (Adult)	20 items/20-80; Clinical significance 39-40	5	Baseline
Anxiety – State	STAI –State Form (Adult)	20 items/20-80; Clinical significance 39-40	5	Baseline, 4 & 8 wks
Depression	PROMIS Depressive Symptoms Parent Proxy	6 items	2	Baseline, 4 & 8 wks
HAI Perceptions	Open Ended Interview		15	End of Study

**Data Management.** [name] (Co-I, VUSN biostatistician) will provide support for: (a) the development of REDCap database for study measures and materials, (b) data management, and (c) statistical analyses.

Participation status will be tracked for all enrolled child/parent participants, and monthly 'Expectation Reports' indicating outstanding assessments will minimize loss of data. Information (e.g., age, reason for non- participation) from eligible participant who do not consent will only be used in summary form to describe the recruitment process. Team training will include all investigators and staff at the initial team meeting and booster sessions as needed to ensure data collection consistency, quality assurance, and intervention fidelity. The PI will provide study manuals, including scripts with instructions, and lead bi-weekly team meetings to maximize recruitment, fidelity, and safety. Questionnaires will be

electronically administered in a standard order with written instructions. Study coordinator or research assistant help will be available in-person to clarify instructions to participants and answer any questions about items. [name] will develop scoring programs and score all measures. Item ranges, and missing and unusual values, will be double-checked.

**Statistical Analysis.** Analysis of the feasibility and preliminary effects of human-animal interactions (HAI) on child and parent stress, depression, anxiety, and quality of life will be conducted using SPSS and STATA statistical software. Descriptive statistical and graphical methods will be used to summarize and visualize patterns in the study outcome data distributions at each time of assessment. Simple group comparisons of participation and retention (e.g., differences in demographic, clinical characteristics) will be conducted using Chi-Square tests of independence and Mann-Whitney tests. Reliable change indices (RCI) will provide the critical foundation for summarizing and analyzing overall efficacy, as well as characteristics of the participants most likely to benefit from HAI in future work. While effect sizes will be more important than statistical significance in this feasibility study, all tests of statistical significance will maintain a maximum  $p < .05$ .

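### One-group pilot rests efficacy and who benefits on reliable change indices: no mean change with a confidence interval is planned, and the missing comparator is not stated as a limit

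*Combined protocol and SAP*

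**What the plan says.** The Overview describes one group: "Children and parent dyads will receive HAI intervention and complete measures of anxiety" and other outcomes at baseline, 4 weeks and 8 weeks. No control arm, wait-list or run-in period is described anywhere. The stated purpose is causal: "We will determine the effects of HAI on reducing anxiety, depression, worry, and pain and enhancing QoL in children". Aim 2 is softer: "Determine the preliminary efficacy of HAI sessions".

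The Statistical Analysis section calls RCI the "critical foundation for summarizing and analyzing overall efficacy, as well as characteristics of the participants most likely to benefit from HAI in future work". Apart from RCI, it plans these items for outcomes:
- descriptive and graphical summaries at each visit;
- effect sizes, which rank above significance but have no stated type, time contrast or interval;
- a .05 ceiling on p-values.

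The only tests it names (Chi-Square and Mann-Whitney) are for participation and retention. RCI is supported by references 44-46, without a formula or cut-off in the text.

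The Summary, Limitations, and Future Directions section says the focus is to estimate reliably which children and parents benefit most. The limitation it gives is generalizability beyond advanced cancer. The missing comparator is not mentioned.

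**The concern.** An RCI asks whether one person's change is larger than measurement error would explain. It does not ask what caused the change, and it does not give the average change or its precision, which a later trial would need for planning.

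The results are meant to feed a multi-site grant. Three things are at stake:
- A count of reliable improvers can be read as an HAI effect when ordinary fluctuation or natural change produced it.
- If the counts become the main result, a real average change is more easily missed than it need be.
- A profile of who benefits can be an artefact of how change scores behave and be carried into the next study.

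**Working it through.** **The plan's own figures.** The documents give no power, effect size or precision figure for efficacy. The sample-size arithmetic reproduces closely: 30/(1 − 0.35) = 46.2, so 47 against the stated 48. In Table 1, 48 × 0.85 = 40.8 (stated 40) and 40 × 0.75 = 30.

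**Inputs.** From the documents: n = 30, and Cronbach's alpha .82 to .87 for the child anxiety scale (Measures, Aim 2). Assumed: a standard RCI, that is change / (SD × √(2(1 − reliability))); alpha used as the reliability; normal scores with equal SDs; and an 8-week correlation r of 0.5 to 0.7 when there is no effect.

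**Step 1: labels under no effect, if RCI classifies.** Cut-off = 1.96 × √(2(1 − reliability)) = 1.18 SD (.82) or 1.00 SD (.87). Share labelled improved = 1 − Φ(cut-off / √(2(1 − r))):

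| Reliability | r = 0.5 | r = 0.6 | r = 0.7 |
|---|---|---|---|
| .82 | 12.0% | 9.4% | 6.4% |
| .87 | 15.9% | 13.2% | 9.8% |

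The same share is labelled deteriorated. In 30 children that is about 2 to 5 each way. If the reliability used equals the retest correlation, each share is the nominal 2.5%.

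**Step 2: power for a true 0.5 SD change at n = 30, by simulation.**
- Paired t-test on mean change: about 75%, 84% and 93% for r = 0.5, 0.6 and 0.7.
- t-test on classes scored +1/0/−1: about 55% to 73% across the six combinations. It rejects 4% to 5% of the time under no effect, so the comparison is fair.
- Exact sign test on improved against deteriorated: about 40% to 60%. It rejects only 0.5% to 2.2% under no effect, so part of its shortfall is conservatism.
- Continuous RCI: no loss, because it is the change score divided by a constant.

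**Step 3: precision of mean change.** Half-width of the 95% CI = t(.975, 29) × √(2(1 − r)/30) = 0.37, 0.33 and 0.29 SD for r = 0.5, 0.6 and 0.7.

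**Step 4: natural change affects both summaries.** A natural 0.3 SD shift with no HAI effect makes mean change significant in 36%, 43% and 54% of studies. A natural 0.5 SD improvement labels 19% to 25% (.82) or 26% to 31% (.87) as improved, about 6 to 9 of 30.

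**Step 5: who benefits, under no effect.** The correlation between baseline score and improvement on the same scale is √((1 − r)/2) = 0.50, 0.45 and 0.39. At n = 30 it is significant in 83%, 72% and 58% of studies. A characteristic tied only to the stable level of the score stays at the nominal 5%. If the analysis then adjusts for baseline, that characteristic (correlation 0.5 to 0.7 with the stable level) gives 17% to 42% false positives, so adjustment is not a cure.

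**Step 6: which model.** A random intercept alone assumes equal correlation between all visits. If correlation is 0.7 to 0.8 over 4 weeks and 0.5 over 8 weeks, a nominal 95% CI at week 8 covers only about 87% to 90% of the time.

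**Step 7: loss.** Table 1 implies 40 − 30 = 10 of 40 without week-8 data. The Eligibility Criteria and Recruitment section allows up to 35% of 48, which is 0.35 × 48 = 16.8, or about 17.

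**The case against.** The strongest reply is that this is a feasibility pilot whose claims are already tempered: efficacy is preliminary, the study is called exploratory, and effect sizes rank above significance. Some group-level estimate is evidently intended. This limits the weight of the point, but the effect size still has no definition and no interval, and RCI is still named as the foundation.

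Several stronger readings are tempting, and the documents do not support them.
- *The missing comparator is a reason to prefer mean change.* It is not. Mean change absorbs natural change just as RCI does (Step 4).
- *The plan will lose power.* Only if RCI is used to classify. The plan does not say so and names no sign test, and references 44-46 may define a version that does not classify.
- *The plan will find a false predictor.* No predictors of benefit are named. The artefact arises if the baseline score on the same scale is examined; it does not affect every characteristic.
- *Regression to the mean inflates the group result*, or, conversely, *cannot affect it.* Entry requires no minimum score: "Exclusion criteria for both children and caregiver include a self-reported fear of or allergies to canines or cognitive impairment" and inability to complete consent are the exclusions. But children enter with relapsed, recurrent or refractory disease, and the timing of baseline relative to such events is not given. If baseline falls at a time of raised distress, the group mean can drift back. The documents settle it neither way.

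**Conclusion.** The point holds as a should-fix matter with two separate parts.

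The first needs no assumption. With one group, neither RCI nor mean change can attribute change to HAI, so the wording on determining effects, on overall efficacy and on reliable estimates of who benefits claims more than the design can give. The limitations text should say so.

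The second is a better choice of main summary. Mean change gives an average and its precision, about ±0.29 to 0.37 SD at n = 30. Its power advantage (about 75% to 93% against 55% to 73% for a 0.5 SD change) depends on RCI being used to classify. The 58% to 83% false-positive rate depends on the same-scale baseline score being examined as a marker of benefit. All these figures rest on the assumed 8-week correlation of 0.5 to 0.7; those for classification also rest on a standard RCI with alpha as the reliability.

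**What to change.** 1. **Main Aim 2 summary.** For each questionnaire score taken at all three visits, report mean change from baseline at weeks 4 and 8 with a 95% CI.
   - *Scores:* child state anxiety; PedsQL General; PedsQL Cancer and its worry and pain subscales; child PROMIS depression; both PedsQL parent proxies; the PROMIS parent proxy; and adult state anxiety. State that heart rate, blood pressure and the biomarkers are outside this list.
   - *Model:* a repeated-measures model with time as a factor and an unstructured covariance, or paired change as a simple alternative. Do not use a random intercept alone.
   - *Data:* in the model, use all enrolled participants with any data. State that this does not remove bias from loss that depends on unobserved scores.
   - *Presentation:* give the 10 scores × 2 times = 20 results as estimates, not confirmatory tests. If nothing changed, about 20 × 0.05 = 1 interval would still exclude zero.
2. **RCI.** Keep it as a secondary description. State its version, reliability source, SD and cut-off, and always show improved and deteriorated together.
3. **Claim.** Report change during 8 weeks of HAI, not efficacy, and list the lack of a comparator in the limitations.
4. **Who benefits.** Label these analyses exploratory, and change reliable to exploratory where the Summary section describes these estimates. Do not interpret the same-scale baseline score as a predictor of benefit. If baseline adjustment is used, show adjusted and unadjusted results side by side with the caution in Step 5.

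The cost is wording plus one standard model per score in the planned software, with no new data, visits or participants. The downside is a more modest claim. The change does not supply a comparator.
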